2.2	27 January 2025	Substantial	Abstract, Figure 1 Study Schematic, Section 9.2.1, and Section , and 9.7.3	Voxelotor allowable treatment gap updated from 30- days to 45 days and required continuous enrollment of insurance and continuous voxelotor exposure 180- days after index.	Exploratory analysis prior to endpoint assessment revealed ~25-30% of voxelotor patients did not receive more than 30 days of treatment, which can bias the follow up times between the study groups. Providers often titrate patients when starting voxelotor, so a larger treatment gap allows us to keep more of these patients.

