9.2. Setting

The study population will include US patients with SCD between the ages of 12 and 85 years who are enrolled in a health insurance plan (commercial, Medicare, Medicaid) continuously during the 365 days prior to and including the index date (baseline) and 180 days post-index. The index selection period is November 25, 2019 (date of Food and Drug Administration [FDA] accelerated approval for voxelotor) through January 31, 2023. The exposed group will include patients with a new prescription claim for voxelotor (no prior use 365 days prior to index date), while the control group will include matched patients who do not have a prescription claim for voxelotor. Non-voxelotor controls will include those receiving no SCD-modifying therapies as well as those receiving non-voxelotor SCD treatments to be reflective of clinical practice. Patients who have a history of stroke will be excluded from this analysis. Both the exposed and control groups may be treated with other SOC treatments such as HU and have 2 or more documented RBC transfusions prior to study index.

Depending on the source of information, approximately 50% of individuals with SCD in the US have received a RBC transfusion, and approximately 20% have received a transfusion in the past year. ¹⁶ In the feasibility assessment of Komodo Healthcare Map (KHM) dataset, race/ethnicity was documented for 90% (n=2230/2486) of patients with 87% (n=1929/2230) identifying as Black or African American. The Centers for Disease Control and Prevention (CDC) estimates 90% of individuals with SCD in the US are non-Hispanic Black or African American. ¹⁷ Socioeconomic status also plays an important factor in impacting patient behavior and access to care. While the KHM dataset does not have direct measures of patients' socioeconomic status, important indicators will be leveraged in the analysis for patients including geography by region, health insurance type, and whether a hematologist is involved in the patient's care. KHM is nationally representative of individuals with SCD. In the Komodo data, approximately 68% of patients have Medicaid as their primary insurance type.

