9.2.1. Inclusion Criteria

Table 2. Summary of Inclusion Criteria

Inclusion Criteria	Assessment Period	Operational Definition	Rationale/Validated Source
Confirmed diagnosis of SCD	[Baseline]	1 inpatient medical claim with an International Classification of Diseases (ICD), Tenth Revision, Clinical Modification (ICD-10-CM) diagnosis code for SCD or 2 outpatient claims with an ICD-10-CM diagnosis code for SCD at least 30 days apart (including all genotypes as well as unknown type)	Administrative claims study ²⁰
Age between 12 and 85 years	[Index]	Age in years since year of birth	Age range covers the initial accelerated approval indication.
≥ 2 RBC transfusions	[Baseline]	At least 2 medical claims with an ICD Tenth Revision, Procedure Coding System (ICD-10-PCS) procedure code for an RBC transfusion at least 1 day apart (maximum 1 transfusion counted per day).	The subset of SCD patients who would most benefit from a reduction in RBC transfusion and necessary to measure a change from baseline to follow-up.
≥ 365 days of continuous enrollment during baseline and at least 180 days in follow up	[Baseline] [Follow Up	Both medical and pharmacy enrollment is required for observability (with a 45-day allowable gap between claims).	Observability is required to assess whether outcomes occurred and were not assumed to be missing.
≥ 180 days of continuous voxelotor use post-index (with 45-day gaps allowed) – voxelotor arm only	[Follow up]	At least 180 days of continuous voxelotor use post-index (with 45-day gaps allowed) defined using the voxelotor ship date and days supply reported on the claim— voxelotor arm only	Adequate exposure to voxelotor is necessary to evaluate the impact on RBC transfusions and other outcomes.

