9.7.3. Outcome Analysis

Operational definitions for each outcome are described below. Each outcome will be assessed using the primary assessment method for the follow-up period where follow-up will end on the earliest of the following occurrences:

- Disenrollment from health insurance (with a 45-day allowable gap)
- Death
- Discontinuation of voxelotor (with a 45-day allowable treatment gap, voxelotor arm only)
- End of follow-up: up to 1 year from index date (365 days)
- The occurrence of any exclusion criteria events (e.g., pregnancy, stroke, hemodialysis, evidence of HSCT or gene therapy, renal transplant, or liver transplant)

The primary analyses will employ an as-treated follow-up approach that ends follow-up upon treatment changes. Patients will be followed from the index date until treatment change (discontinuation of voxelotor for voxelotor group), or the end of follow-up, whichever is earlier. This as-treated method of analysis allows for an estimate of the effect while the patient is taking the drug of interest and addresses intercurrent events. However, it may introduce bias into the estimates. To adjust for differences in follow-up time between voxelotor patients and their matched controls, matched or pairwise censoring will be applied to censor unexposed on the date of voxelotor discontinuation for their matched pair as a sensitivity analysis.³⁸ A summary of sensitivity analyses is included in Table 7 to evaluate how the magnitude of this bias will be assessed.

Primary Objective - Change in Number of RBC Transfusions PPPY

For each patient, the difference in the number of RBC transfusions PPPY from baseline to follow-up period will be reported as the change and will be calculated as follows:

$$Change = \left(\frac{Number\ of\ RBC\ transfusions\ in\ follow-up}{Available\ days\ of\ follow-up} - \frac{Number\ of\ RBC\ transfusions\ in\ baseline}{365\ days\ *}\right)x\ 365$$

The change in the number of RBC transfusions PPPY will be analyzed using generalized linear model (GLM) with an identity link to estimate the difference in RBC transfusion change rates between the two groups. If any pre-index covariates that are found to be unbalanced after the PS method, it will be included in the regression as a covariate. The rate change and its 95% confidence intervals (CI) will be reported.

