$$Percent Change = \frac{(\frac{Number \ of \ RBC \ transfusions \ in \ follow - up}{Available \ days \ of \ follow - up} - \frac{Number \ of \ RBC \ transfusions \ in \ baseline}{365 \ days \ *} x \ 100}{\frac{Number \ of \ RBC \ transfusions \ in \ baseline}{365 \ days \ *}}$$

*All patients have 365 days of baseline data

The mean percentage change in the number of RBC transfusions PPPY within each group will be reported. The proportion of patients with a 30% reduction in RBC transfusions will also be reported for each group. A logistic regression model will be used to compare the difference of the proportion of patients with the reduction of more than 30% between the groups with an estimated odds ratio. The 95% CIs will also be reported.

Exploratory Objective 2 Endpoint 3 – Proportion of Patients with Zero RBC Transfusions PPPY in Follow-Up

This outcome will be defined as the proportion of patients with zero RBC transfusions PPPY during follow-up. A logistic regression model will be used to compare the percentage of patients without a transfusion in the follow-up time frame between the groups and an odds ratio will be estimated. The 95% CIs will also be reported.

Exploratory Objective 3 – Time to Transfusion-Associated Complications

Each RBC-associated complication (including the composite outcome) will be assessed as a time-to-event outcome. Cox PH models will be used to calculate the HR; 95% CIs will be calculated using a robust variance estimator. The Cox PH regression model may incorporate confounders that remain unbalanced after PS adjustment.

Sensitivity and Subgroup Analyses

Table 7 below includes a summary of the sensitivity analyses and the rationale for performing each analysis. The following sensitivity analyses will be performed for the primary endpoint unless otherwise specified:

Table 7. Planned Sensitivity and Subgroup Analyses

Analysis	Description	Rationale
Intention-to-Treat (ITT)	The follow-up period will be changed from astreated to follow an ITT approach with the exposed group requiring at least one voxelotor claim. All patients will be followed from the index date until disenrollment, death, or end of study period. Follow-up will not end on treatment discontinuation or switches.	To estimate the effect of the "assigned" treatment.

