Required 1-year minimum follow-up	Two subgroup analyses have been proposed to evaluate bias introduced by differential follow-up. First, a subgroup analysis of patients with a minimum of 1-year of follow-up will be performed to evaluate the impact of informative censoring.	To address the impact of informative censoring and differential follow-up
Matched censoring	If meaningful differences in follow-up time are observed, matched censoring will be performed to assess the impact of differential follow-up between the exposed and referent group for the primary objective. Bias due to differential follow-up can arise when the reasons for participants dropping out or being lost to follow-up are related to both the treatment and the outcome. Matched censoring mitigates this bias by censoring all patients within a matched set (i.e., patients that have been matched by PS matching) at the earliest time in which a patient in the set was censored. In the context of 1:2 PS matching, where each exposed patient is matched to two referent patients, the matched set will consist of at most three individuals. Thus, matched censoring in this scenario involves censoring data for all three individuals in a matched set at the earliest observed censoring time among them.	To address the impact of informative censoring and differential follow-up
Stratification by number of RBC transfusions in baseline	The number of RBC transfusions PPPY in baseline will be categorized and the primary objective will be reported separately for those categories. This analysis will be performed for all objectives.	To understand the effect of the treatment on high-risk subgroups.
Subgroup analysis by Hb level	The primary analysis will also be performed on a subgroup of patients with Hb values at baseline. A separate PS model will be utilized for this subgroup.	To understand the effect of the treatment on high-risk subgroups and patients with available baseline data.
Subgroup analysis by prior medications	A subgroup analysis will be performed on patients who received hydroxyurea, crizanlizumab, L-glutamine, and/or ESA in baseline the exposed and referent groups.	To understand the effect of other SCD treatments.

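### Only the voxelotor arm must complete 180 days of use after index while outcomes count from day 1, so the primary estimate mixes drug effect with selection of persisters

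*Protocol*

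**What the plan says.** Protocol Section 9.2.1, Table 2, sets two conditions that can only be checked after the index date.

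- Voxelotor arm only: "At least 180 days of continuous voxelotor use post-index (with 45-day gaps allowed) defined using the voxelotor ship date". The stated reason is that "Adequate exposure to voxelotor is necessary to evaluate the impact on RBC transfusions and other outcomes".
- Both arms: "≥ 365 days of continuous enrollment during baseline and at least 180 days in follow up".

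Controls have no persistence condition. Section 9.2 says "the control group will include matched patients who do not have a prescription claim for voxelotor", with no time limit given, so an initiator removed by the use criterion does not become a control either.

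Outcome counting does not wait for day 180. Figure 1 starts the outcome window on day 1, and Section 9.7.3 says "Patients will be followed from the index date until treatment change" or the end of follow-up.

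Section 5 gives the background to the use criterion: an exploratory look found that about "25-30% of voxelotor patients did not receive more than 30 days of treatment".

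Table 7 (Section 9.7.3) lists the checks. The 1-year-minimum analysis is described as "a subgroup analysis of patients with a minimum of 1-year of follow-up will be performed to evaluate the impact of informative censoring". Matched censoring cuts each matched set at its earliest censoring time. The ITT analysis asks only for one voxelotor claim in the exposed group, and "All patients will be followed from the index date until disenrollment, death, or end of study period".

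**The concern.** In the voxelotor arm, the first 180 days both decide who is in the study and supply outcome data. An initiator who stops on day 90 is deleted together with every transfusion up to that day. A control with the same course stays in and is counted. If the reason for stopping has anything to do with how the patient is doing, the retained voxelotor patients no longer represent those who started the drug, and the controls do not represent their untreated counterpart.

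The planned safeguards do not reach this step:

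- Propensity scores use baseline data and cannot balance a selection made afterwards.
- Matched censoring works on patients already selected.
- The 1-year-minimum subgroup keeps only patients with complete follow-up, so it selects harder on the same feature.
- Sections 9.7.3 and 9.9 concede possible bias from as-treated censoring and unequal follow-up, but not from this entry criterion.

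Only the ITT analysis appears to lift the criterion. It does not say so outright, and it states no 365-day limit although the objective is framed as up to one year.

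This affects the primary estimate, which Section 7 says is meant to inform marketing authorization decisions. The exploratory endpoints use the same cohort, so they lose early events in the voxelotor arm wherever the event leads to stopping.

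**Working it through.** **The plan's own figure.** Section 9.5 gives 185 treated and 370 controls for a difference of 1 transfusion PPPY, SD 3.0, 80% power and an adjustment factor of 1.65. Alpha is not stated there; two-sided 0.05 is assumed from the 95% confidence intervals.

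- Treated n = (1 + 1/2) × 3.0² × (1.960 + 0.842)² / 1² = 106; × 1.65 = 174.9, so 175 and 350.
- The stated 185 and 370 are slightly larger and give about 82% power. The difference is on the safe side, and the present point does not depend on it.

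**Standard error at the planned size.** SE = 3.0 × √1.65 × √(1/185 + 1/370) = 0.347.

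**Bias under no drug effect.** Let f be the share of initiators removed, and D the mean change in removed patients minus the mean change in retained patients (positive D means the removed do worse). With no effect and good baseline balance, all initiators together have the control mean: μ = (1 − f) × m(retained) + f × m(removed). Therefore m(retained) − μ = −f × D.

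Chance of a significant result favouring voxelotor = Φ(−1.96 − bias/SE):

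| f | D | Bias (PPPY) | False significant benefit |
|---|---|---|---|
| 0.25 | 0 | 0 | 2.5% |
| 0.25 | +1 | −0.25 | 11% |
| 0.25 | +2 | −0.50 | 30% |
| 0.30 | +1 | −0.30 | 14% |
| 0.30 | +2 | −0.60 | 41% |
| 0.25 to 0.30 | −1 | +0.25 to +0.30 | below 0.5% |

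Both f and D are assumptions. The range for f borrows the early-stopping figure in Section 5. The documents give no value for D.

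**Cross-checks, also with assumed links, f = 0.30.**

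- Normal selection model, correlation ρ between change and stopping: bias = −ρ × 3.0 × φ(0.524)/0.70 = −ρ × 3.0 × 0.497. For ρ = 0.1, 0.2 and 0.3 this is −0.15, −0.30 and −0.45.
- Count simulation (gamma-distributed patient rates, at least 2 baseline transfusions, SD of log-rate change 0.4), standardised on baseline count: odds ratios of stopping of 1.0, 1.1, 1.25 and 1.5 per transfusion in days 1-180 give about 0, −0.17, −0.40 and −0.69. An odds ratio of 0.8 gives +0.32.

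**Would a landmark repair it?** In the same simulation at odds ratio 1.25, keeping the filter but counting outcomes only after day 180 moves the bias from −0.40 to −0.26. It shrinks but remains, because entry still depends on one-sided persistence.

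**The case against.** A reader might infer that the design must favour voxelotor. The documents do not support that. Transfusion is a repeatable count, so the filter does not make the first 180 days event-free. The direction depends on why patients stop, which the protocol does not report. The only documented early stoppers had 30 days of treatment or less. At an assumed 4 to 6 transfusions a year, they would expect about 0.3 to 0.5 transfusions in that time (4 × 30/365 to 6 × 30/365), which is little transfusion response to act on. This objection stands, and the claim is conditional for that reason.

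A reader might also take 25-30% as the minimum share removed. That figure was seen under the earlier 30-day gap rule, and the gap was widened to 45 days partly to retain such patients. The share failing the current rule is unknown.

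Three further limits stand:

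- The 180-day enrolment rule applies to both arms and is not one-sided.
- Controls must have no voxelotor claim, with no time limit stated. If worsening controls later start the drug and are dropped, this could flatter the control arm.
- Stroke ends follow-up in both arms, so transfusions after a stroke are not counted against controls.

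The sponsor can also say that the target is the effect while on drug, that the ITT analysis already covers all initiators, and that including early stoppers costs power. If 25-30% gain nothing, a 1-unit effect dilutes to 0.75-0.70 and power at 185/370 falls to about 58-52%. That loss belongs to the ITT analysis. An index-defined cohort that keeps as-treated censoring still estimates an on-drug effect and does not count time after stopping. An on-drug target also does not require deleting patients for what happens after time zero.

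**Conclusion.** The structural flaw is established from the text: a post-index use criterion in one arm, outcome counting from day 1, and no planned adjustment in the primary analysis that can remove the resulting selection. Its direction and size are not established.

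The bias favours voxelotor only if early stoppers have a worse transfusion change. If 25-30% are removed and D is 1 to 2 PPPY, the spurious difference is 25-60% of the effect the study is sized to detect. With D = 0 there is no bias, and with negative D it works against voxelotor. Because the protocol does not plan to report what would distinguish these cases, a favourable primary result could not be read as a drug effect alone. The point should be settled before the primary result is interpreted.

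**What to change.** 1. Define the primary cohort on information available up to the index date. Remove the 180-day use criterion from Table 2, and the 180-day post-index enrolment criterion with it (the latter affects both arms).
2. Keep the stated as-treated censoring from day 1. Weight by person-time, because one transfusion in 30 days annualises to 365/30 = 12.2 PPPY and would otherwise dominate. Person-time weighting again gives persisters more influence, so add inverse-probability-of-censoring weights, using transfusions updated over time, to handle informative stopping.
3. Keep the 180-day persister cohort as a sensitivity analysis, and do not present the 1-year-minimum subgroup as a test of informative censoring.
4. State that the ITT analysis drops the use criterion, and cap it at 365 days to match the one-year endpoint.
5. Report how many initiators the use criterion removes, and their outcomes.
6. Do not rely on a day-181 landmark as the repair.

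The cost is a protocol amendment and a re-run on data already held. The estimate will be somewhat noisier and possibly less favourable. In the ITT analysis, dilution by early stoppers would lower power; under the no-benefit assumption above, 80% power would need about 311 to 357 treated patients at 1:2.

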9.2.2. Exclusion Criteria

Table 3. Summary of Exclusion Criteria

Exclusion Criteria	Assessment Period	Operational Definition	Rationale/Validated Source
Stroke or history of stroke	[Baseline]	At least one medical claim with an ICD-10- CM diagnosis code with evidence of stroke.	This study is intended to be generalizable to SCD patients. Patients with a history of stroke may rely on RBC transfusions for disease management and will therefore be excluded.
Pregnancy	[Baseline]	At least one medical claim with an ICD-10- CM diagnosis code with evidence of pregnancy	This study is intended to be generalizable to SCD patients and this is a common exclusion for RCTs. Individuals with SCD may receive RBC transfusions to ensure adequate oxygenation of the fetus during pregnancy. Voxelotor is not indicated during pregnancy.
Hemodialysis or history of hemodialysis	[Baseline]	At least one medical claim with an ICD-10- PCS procedure code with evidence of hemodialysis.	Patients with a history of hemodialysis may rely on RBC transfusions for disease management and will therefore be excluded.
Hematopoietic stem cell transplantation (HSCT) or gene therapy or history of HSCT or gene therapy	[Baseline]	At least one medical claim with an ICD-10-PCS procedure code with evidence of HSCT or gene therapy.	Patients with a history of HSCT may rely on RBC transfusions for disease management and will therefore be excluded. After HSCT or gene therapy, their disease may be markedly improved.

Renal transplant or history of renal transplant	[Baseline]	At least one medical claim with an ICD-10- PCS procedure code with evidence of renal transplant.	Patients with a history of renal transplants may rely on RBC transfusions for disease management and will therefore be excluded.
Liver transplant or history of liver transplant	[Baseline]	At least one medical claim with an ICD-10-PCS procedure code with evidence of liver transplant.	This study is intended to be generalizable to SCD patients. Patients with a history of liver transplants may rely on RBC transfusions for disease management and will therefore be excluded.
Iron overload - Exploratory Objective 3 Subgroup Only	[Baseline]	At least one medical claim with an ICD-10- CM diagnosis code with evidence of iron overload	To assess incident events in follow-up for Exploratory Objective 3
Iron chelation use - Exploratory Objective 3 Subgroup Only	[Baseline]	At least one pharmacy claim with an NDC or medical claim with an HCPCS/CPT for iron chelation	To assess incident events in follow-up for Exploratory Objective 3
DHTR - Exploratory Objective 3 Subgroup Only	[Baseline]	At least one medical claim with an ICD-10- CM diagnosis code with evidence of DHTR	To assess incident events in follow-up for Exploratory Objective 3
Alloimmunization - Exploratory Objective 3 Subgroup Only	[Baseline]	At least one medical claim with an ICD-10- CM diagnosis code with evidence of alloimmunization	To assess incident events in follow-up for Exploratory Objective 3

9.3. Variables

The exposure of interest (i.e., voxelotor) will be defined using Claritas prescription data, lab assessments (i.e., Hb labs) will be defined using Quest Diagnostics data, and all other study variables will be defined using KHM database closed claims. See Section 9.4 for full

description of the data that will be used for this study. A list of variables for the study is outlined in Table 4 and the endpoints are described in Table 5. The operational definition for each variable listed in Tables 4 and 5 is provided in Annex Table 1. All variables on medical history, covariates, and endpoints of interest will be identified with ICD-10-CM diagnosis/procedure codes and Healthcare Common Procedure Coding System (HCPCS) codes in inpatient and or outpatient medical claims, and with National Drug Codes (NDC) in prescription claims. All codes and/or code algorithms will be reviewed by all protocol authors as well as the study Scientific Review Committee.

When possible, validated algorithms in administrative claims data will be used to define the study variables. For the primary and exploratory outcomes, RBC transfusions will be defined using procedure codes from medical claims and evaluated as a maximum of 1 per day. RBC transfusions are assumed to be documented accurately because healthcare entities must bill to receive reimbursement.²¹ A literature review was conducted on the validity of RBC transfusions in RWD such as claims and electronic health records (EHR) prior to drafting the protocol and results were consistently positive.^{22–26}

Table 4. List of Variables, Roles, and Assessment Period

Variables	Role	Assessment period	Output
Age	Baseline Characteristic; Covariate	[Index]	Continuous: Mean (SD); Median (IQR); Minimum; Maximum. Frequency and proportion (N, %) of patients with missing values will also be reported.
Sex	Baseline Characteristic; Covariate	[Index]	Frequency and proportion (N, %) Categorical: Male, Female, Unknown, Missing
Race/ethnicity	Baseline Characteristic; Covariate	[Index]	Frequency and proportion (N, %) Categorical: White, Black or African American, Asian or Pacific Islander, Hispanic or Latino, Other, Unknown
Insurance Type	Baseline Characteristic; Covariate	[Index]	Frequency and proportion (N, %) Categorical: Medicare, Medicaid,

V2.0 23 December 2024			
			Commercial, Multiple, Other
Region	Baseline Characteristic; Covariate	[Index]	Frequency and proportion (N, %) Categorical: Northeast, Midwest, South, and West Regions (based on Census geographic regions), Missing
Top 10 Diagnosing Provider Specialty	Baseline Characteristic; Covariate	[Baseline]	Frequency and proportion (N, %) [Provider specialty categories will be included in statistical analysis plan (SAP)]
SCD Hematology Diagnosing Provider	Baseline Characteristic; Covariate	[Baseline]	Frequency and proportion (N, %) Binary: Yes, No (including non-hematology and null values)
SCD Genotype ¹	Baseline Characteristic	[Baseline]	Frequency and proportion (N, %) Categorical: Homozygous SS, HbSC, HbSB0 thalassemia, HbSB+ thalassemia, Unknown, Multiple genotypes reported
Comorbidities – SCD specific morbidities ²	Baseline Characteristic; Covariate	[Baseline]	Frequency and proportion (N, %)
Hydroxyurea	Baseline Characteristic; Covariate	[Baseline]; [Follow- up]	Frequency and proportion (N, %)
Crizanlizumab	Baseline Characteristic; Covariate	[Baseline]; [Follow- up]	Frequency and proportion (N, %)
L-glutamine	Baseline Characteristic; Covariate	[Baseline]; [Follow- up]	Frequency and proportion (N, %)
Erythropoietin Stimulating Agent (ESA)	Baseline Characteristic; Covariate	[Baseline]; [Follow- up]	Frequency and proportion (N, %)

V2.0 23 December 2024			
RBC transfusion	Baseline Characteristic; Covariate	[Baseline]; [Follow-up]	Continuous: Mean (SD); Median (IQR); Minimum; Maximum.
Baseline Hb lab test	Baseline Characteristic	[Baseline]	Frequency and proportion (N, %) Categorical: Komodo lab test only, Quest lab test only, Komodo lab test and Quest lab test, No value
Baseline Hb value ³	Baseline Characteristic	[Baseline]	Continuous: Mean (SD); Median (IQR); Minimum; Maximum.
Charlson Comorbidity Index (CCI) ⁴	Baseline Characteristic; Covariate	[Baseline]	Continuous: Mean (SD); Median (IQR); Minimum; Maximum. Frequency and proportion (N, %) For individual categories see SAP.
Healthcare Interactions - Inpatient/Outpatient Visit	Baseline Characteristic; Covariate	[Baseline]	Continuous: Mean (SD); Median (IQR); Minimum; Maximum.
Follow-up time	Baseline Characteristic; Covariate	[Follow-up]	Continuous: Mean (SD); Median (IQR); Minimum; Maximum.
Voxelotor	Exposure	[Index]; [Follow-up]	Frequency and proportion (N, %)
Iron overload	Baseline Characteristic; Covariate	[Baseline]	Frequency and proportion (N, %)
Iron chelation use	Baseline Characteristic; Covariate	[Baseline]	Frequency and proportion (N, %)
Delayed hemolytic transfusion reactions	Baseline Characteristic; Covariate	[Baseline]	Frequency and proportion (N, %)
Alloimmunization	Baseline Characteristic; Covariate	[Baseline]	Frequency and proportion (N, %)
Death	Baseline Characteristic; Covariate	[Follow-up]	Frequency and proportion (N, %)
Voxelotor discontinuation	Baseline Characteristic; Covariate	[Follow-up]	Frequency and proportion (N, %)

Abbreviations: ESA: Erythropoietin Stimulating Agent; RBC: Red blood cell; SCD: Sickle cell disease.

Baseline genotype will not be included in the PS model because patients commonly have multiple values due to coding/billing errors and this value is more likely to be misclassified. The most frequently occurring value (not including unknown/other) will be selected

- 2. SCD-specific comorbidities include the following: acute chest syndrome, acute coronary syndrome, acute osteomyelitis, acute renal failure, aplastic crisis, intracerebral and subarachnoid hemorrhage, myocardial infarction, priapism, splenic sequestration crisis, transfusion-associated reaction, venous thromboembolism, avascular necrosis, cholelithiasis, chronic kidney disease, chronic pain, diabetes, heart failure, iron overload, leg ulcer, pulmonary hypertension, VOC, and retinopathy.
- 6. Given feasibility analyses have indicated a low proportion of patients (<25%) have lab values, Hb will be excluded from the PS model. Hb will be evaluated excluding those measurements within 2 days of an acute event or within 30-60 days of a transfusion event. Full algorithm will be provided in a separate statistical analysis plan.
- 4. CCI categories include: myocardial infarction, congestive heart failure, peripheral vascular disease, cerebrovascular disease, dementia, chronic pulmonary disease, rheumatic disease, peptic ulcer disease, mild liver disease, diabetes without chronic complication, diabetes with chronic complication, hemiplegia or paraplegia, renal disease (mild to moderate), renal disease (severe), any malignancy without metastasis including leukemia and lymphoma, moderate or severe liver disease, metastatic solid tumor, human immunodeficiency virus, acquired immunodeficiency syndrome

The table above includes a summary of baseline characteristics and possible covariates for PS modeling. Covariates will be selected using the diagnostic criteria outlined in the data analysis plan (Section 9.7).

Table 5. Description of Endpoints and Alignment to Study Objectives

Endpoint	Assessment Period	Output	Objective Alignment
Change in RBC transfusions	[Baseline]; [Follow-up]	Mean change in the number of RBC transfusions (maximum 1 per day) PPPY from baseline to follow-up	Primary Objective
VOCs	[Baseline]; [Follow-up]	Mean change in the number of events (maximum 1 per day) PPPY from baseline to follow-up. VOC events need to occur more than 5 days apart to be considered separate events.	Exploratory Objective 1.1
ACS	[Baseline]; [Follow-up]	Mean change in the number of events (maximum 1 per day) PPPY from baseline to follow-up	Exploratory Objective 1.1
ACS Including Pneumonia	[Baseline]; [Follow-up]	Mean change in the number of events (maximum 1 per day) PPPY from baseline to follow-up	Exploratory Objective 1.1
Priapism	[Baseline]; [Follow-up]	Mean change in the number of events (maximum 1 per day) PPPY from baseline to follow-up	Exploratory Objective 1.1

Voxelotor

V2.0 23 December 2024		9	
Stroke (including transient ischemic attack)	[Follow-up]	Time to event during follow-up	Exploratory Objective 1.2
RBC transfusions in follow-up	[Follow-up]	Mean number of RBC transfusions (maximum 1 per day) PPPY in follow-up	Exploratory Objective 2
Percent reduction in RBC transfusion > 30%	[Baseline]; [Follow-up]	Proportion of patients with a percentage decrease in the number of RBC transfusions (maximum 1 per day) PPPY from baseline to follow-up that is greater than 30%	Exploratory Objective 2
Zero RBC transfusions in follow-up	[Follow-up]	Proportion of patients with 0 RBC transfusions (maximum 1 per day) PPPY during follow- up	Exploratory Objective 2
Iron overload	[Follow-up]	Time to event during follow-up	Exploratory Objective 3
Iron chelation use	[Follow-up]	Time to event during follow-up	Exploratory Objective 3
Delayed hemolytic transfusion reactions	[Follow-up]	Time to event during follow-up	Exploratory Objective 3
Alloimmunization	[Follow-up]	Time to event during follow-up	Exploratory Objective 3
Composite outcome (iron overload, iron chelation use, delayed hemolytic transfusion reactions, and/or alloimmunization)	[Follow-up]	Time to event during follow-up	Exploratory Objective 3

Abbreviations: ACS: Acute Chest Syndrome; PPPY: per patient per year; RBC: Red blood cell; VOC: vaso-occlusive crisis The table above includes a summary of the outcomes of interest for this analysis. Operational definitions can be found in the data analysis plan (Section 9.7).

